6.10. Previous and Concomitant Therapy

Summaries of previous and concomitant medications will be based on the ITT population.

At screening, previous and current AD treatments are recorded for each patient. Concomitant therapy for the treatment period is defined as therapy that starts before or during the treatment period and ends during the treatment period or is ongoing (has no end date or ends after the treatment period). Should there be insufficient data to make this comparison (for example, the concomitant therapy stop year is the same as the treatment start year, but the concomitant therapy stop month and day are missing), the medication will be considered as concomitant for the treatment period.

Summaries of previous medications will be as follows:

- Previous AD therapies

Summaries of concomitant medications will be as follows:

- Concomitant medications excluding rescue medicine

6.11. Efficacy Analyses

The general methods used to summarize efficacy data, including the definition of baseline value for assessments are described in Section 6.2. The censoring rules applied to data as well as imputation methods are described in Section 6.4.

[Table JAHL.6.4](#) provides the descriptions and derivations of the primary, secondary, and exploratory efficacy outcomes.

[Table JAHL.6.5](#) provides the detailed analyses including analysis type, method and imputation, population, time point, and comparisons for efficacy analyses.

Table JAHL.6.4. Description and Derivation of Primary, Secondary and Exploratory Efficacy Outcomes

Measure	Description	Variable	Derivation / Comment	Imputation Approach if Missing Components
Validated Investigator's Global Assessment for AD (IGA)	The validated Investigator's global assessment of the patient's overall severity of their AD, based on a static, numeric 5-point scale from 0 (clear) to 4 (severe). The score is based on an overall assessment of the degree of erythema, papulation/induration, oozing/crusting, and lichenification.	IGA score	Single item. Range: 0 to 4 0 represents "clear" 4 represents "severe"	Single item, missing if missing.
		Change from baseline in IGA score	Change from baseline: observed IGA score – baseline IGA score	Missing if baseline or observed value is missing.
		
 ▪ IGA [0,1] with ≥ 2-point improvement ▪ IGA [0] 	
 ▪ Observed score of 0 or 1 and change from baseline ≤ -2 ▪ Observed score of 0 	
 ▪ Missing if baseline or observed value is missing. ▪ Single item, missing if missing.
Eczema Area and Severity Index (EASI)	The EASI assesses objective physician estimates of 2 dimensions of atopic dermatitis – disease extent and clinical signs (Hanifin et al 2001) – by scoring the extent of disease (percentage of skin affected: 0 = 0%; 1 = 1-9%; 2 = 10-29%; 3 = 30-49%; 4 = 50-69%; 5 = 70-89%; 6 = 90-100%) and the severity of 4 clinical signs (erythema, edema/papulation, excoriation, and lichenification) each on a scale of 0 to 3 (0 = none, absent; 1 = mild; 2 = moderate; 3 = severe) at 4 body sites (head and neck, trunk, upper limbs, and lower limbs). Half scores are allowed between severities 1, 2 and 3. Each body site will have a score that ranges from 0 to 72, and the final EASI score will be obtained by weight-averaging these 4 scores. Hence, the final EASI score will range from 0 to 72 for each time point.	EASI score	Derive EASI region score for each of head and neck, trunk, upper limbs, and lower limbs as follows: $\text{EASI}_{\text{region}} = (\text{Erythema} + \text{edema/papulation} + \text{Excoriation} + \text{Lichenification}) * (\text{value from percentage involvement})$, where erythema, edema/papulation, excoriation, and lichenification are evaluated on a scale of 0 to 3 and value from percentage involvement is on a scale of 0 to 6. Then total EASI score is as follows: $\text{EASI} = 0.1 * \text{EASI}_{\text{head and neck}} + 0.3 * \text{EASI}_{\text{trunk}} + 0.2 * \text{EASI}_{\text{upper limbs}} + 0.4 * \text{EASI}_{\text{lower limbs}}$	N/A – partial assessments cannot be saved.
		
 ▪ Change from baseline in EASI score ▪ Percent change from baseline EASI score 	Change from baseline: observed EASI score – baseline EASI score % change from baseline: $100 \times \frac{\text{Observed score} - \text{Baseline}}{\text{Baseline}}$	Missing if baseline or observed value is missing.
		EASI50	% Improvement in EASI score from baseline $\geq 50\%:$	Missing if baseline or observed value is missing.

			% change from baseline ≤ -50	
		EASI75	% Improvement in EASI score from baseline $\geq 75\%$: % change from baseline ≤ -75	Missing if baseline or observed value is missing.
		EASI90	% Improvement in EASI score from baseline $\geq 90\%$: % change from baseline ≤ -90	Missing if baseline or observed value is missing.
Body Surface Area (BSA) Affected by AD	Body surface area affected by AD will be assessed for 4 separate body regions and is collected as part of the EASI assessment: head and neck, trunk (including genital region), upper extremities, and lower extremities (including the buttocks). Each body region will be assessed for disease extent ranging from 0% to 100% involvement. The overall total percentage will be reported based off of all 4 body regions combined, after applying specific multipliers to the different body regions to account for the percent of the total BSA represented by each of the 4 regions.	BSA score	Use the percentage of skin affected for each region (0 to 100%) in EASI as follows: $\text{BSA Total} = 0.1 * \text{BSA}_{\text{head and neck}} + 0.3 * \text{BSA}_{\text{trunk}} + 0.2 * \text{BSA}_{\text{upper limbs}} + 0.4 * \text{BSA}_{\text{lower limbs}}$	N/A – partial assessments cannot be saved.
		Change from baseline in BSA score	Change from baseline: observed BSA score – baseline BSA score	Missing if baseline or observed value is missing.
SCORing Atopic Dermatitis (SCORAD)	The SCORing Atopic Dermatitis (SCORAD) index uses the rule of nines to assess disease extent (head and neck 9%; upper limbs 9% each; lower limbs 18% each; anterior trunk 18%; back 18%; and genitals 1%). It evaluates 6 clinical characteristics to determine disease severity: (1) erythema,	SCORAD score	$\text{SCORAD} = A/5 + 7B/2 + C$, where A is extent of disease, range 0-100 B is disease severity, range 0-18 C is subjective symptoms, range 0-20	Missing if components A and B are missing or if component C is missing. Partial assessments performed by physician cannot be saved and partial assessments performed by subject cannot be saved.


(2) edema/papulation, (3) oozing/crusts, (4) excoriation, (5) lichenification, and (6) dryness on a scale of 0 to 3 (0=absence, 1=mild, 2=moderate, 3=severe). The SCORAD index also assesses subjective symptoms of pruritus and sleep loss in the last 72 hours on visual analogue scales (VAS) of 0 to 10 where 0 is no itch or sleep loss and 10 is worst imaginable itch or sleep loss. These 3 aspects: extent of disease, disease severity, and subjective symptoms combine to give a maximum possible score of 103 (Stalder et al. 1993; Kunz et al. 1997; Schram et al. 2012).
	
 ▪ Change from baseline in SCORAD score ▪ Percent change from baseline in SCORAD score 	
Change from baseline: observed SCORAD score – baseline SCORAD score
 
% change from baseline: $100 \times \frac{\text{Observed score} - \text{Baseline}}{\text{Baseline}}$
	Missing if baseline or observed value is missing.
	SCORAD75	
% Improvement in SCORAD from baseline $\geq 75\%$:
 
% change from baseline ≤ -75
	Missing if baseline or observed value is missing.
	SCORAD90	
% Improvement in SCORAD from baseline $\geq 90\%$:
 
% change from baseline ≤ -90
	Missing if baseline or observed value is missing.

Table JAHL.6.5. Description of Primary, Secondary and Exploratory Efficacy Analyses

Measure	Variable	Analysis Method (Section 6.2.3)	Population (Section 6.2.1)	Comparison/Time Point	Analysis Type
Validated Investigator's Global Assessment for AD (IGA)	Proportion of patients achieving IGA [0,1] with a ≥ 2 -point improvement	Logistic regression using NRI	ITT	Bari 4-mg or Bari 2-mg vs PBO; Week 16	Primary analysis
				Bari 1-mg vs PBO; Week 16	Key secondary analysis
			PPS	Bari 4-mg or Bari 2-mg or Bari 1-mg vs PBO; Week 16	Sensitivity analysis
			ITT	Bari 4-mg or Bari 2-mg or Bari 1-mg vs PBO; Week 4	Secondary analysis
	Proportion of patients achieving IGA [0]	Logistic regression using pMI and Tipping Point	ITT	Bari 4-mg or Bari 2-mg or Bari 1-mg vs PBO; Week 16	Sensitivity analysis
			ITT	Bari 4-mg or Bari 2-mg or Bari 1-mg vs PBO; Week 16	Secondary analysis
			ITT	Bari 4-mg or Bari 2-mg or Bari 1-mg vs PBO; Week 16	Secondary analysis
			ITT	Bari 4-mg or Bari 2-mg or Bari 1-mg vs PBO; Week 16	Secondary analysis
Eczema Area and Severity Index (EASI)	
 EASI score Change from baseline in EASI score Percent change from baseline in EASI score 	MMRM	ITT	Bari 4-mg or Bari 2-mg or Bari 1-mg vs PBO; Week 16	Key secondary analysis
			PPS	Bari 4-mg or Bari 2-mg or Bari 1-mg vs PBO; Week 16	Sensitivity analysis
		ANCOVA using mLOCF	ITT	Bari 4-mg or Bari 2-mg or Bari 1-mg vs PBO; Week 16	Sensitivity analysis
		pMI and Tipping Point	ITT	Bari 4-mg or Bari 2-mg or Bari 1-mg vs PBO; Week 16	Sensitivity analysis
	
 Proportion of patients achieving EASI50 Proportion of patients achieving EASI75 Proportion of patients achieving EASI90 	Logistic regression using NRI	ITT	Bari 4-mg or Bari 2-mg or Bari 1-mg vs PBO; Week 16	Secondary analysis
		Logistic regression using NRI	ITT	Bari 4-mg or Bari 2-mg or Bari 1-mg vs PBO; Week 16	Key secondary analysis
			PPS	Bari 4-mg or Bari 2-mg or Bari 1-mg vs PBO; Week 16	Sensitivity analysis
		pMI and Tipping Point	ITT	Bari 4-mg or Bari 2-mg or Bari 1-mg vs PBO; Week 16	Sensitivity analysis
Body Surface Area (BSA) Affected by AD	
 BSA score Change from baseline in BSA score 	MMRM	ITT	Bari 4-mg or Bari 2-mg or Bari 1-mg vs PBO; Week 16	Secondary analysis
		ANCOVA using mLOCF	ITT	Bari 4-mg or Bari 2-mg or Bari 1-mg vs PBO; Week 16	Sensitivity analysis

Measure	Variable	Analysis Method (Section 6.2.3)	Population (Section 6.2.1)	Comparison/Time Point	Analysis Type
SCORing Atopic Dermatitis (SCORAD)	
 SCORAD score Change from baseline in SCORAD score Percent change from baseline in SCORAD score 	MMRM	ITT	Bari 4-mg or Bari 2-mg or Bari 1-mg vs PBO; Week 16	Secondary analysis
		ANCOVA using mLOCF	ITT	Bari 4-mg or Bari 2-mg or Bari 1-mg vs PBO; Week 16	Sensitivity analysis
	Proportion of patients achieving SCORAD75	Logistic regression using NRI	ITT	Bari 4-mg or Bari 2-mg or Bari 1-mg vs PBO; Week 16	Key secondary analysis
			PPS	Bari 4-mg or Bari 2-mg or Bari 1-mg vs PBO; Week 16	Sensitivity analysis
		Logistic regression using pMI	ITT	Bari 4-mg or Bari 2-mg or Bari 1-mg vs PBO; Week 16	Sensitivity analysis
	Proportion of patients achieving SCORAD90	Logistic regression using NRI	ITT	Bari 4-mg or Bari 2-mg or Bari 1-mg vs PBO; Week 16	Secondary analysis
		pMI and Tipping Point	ITT	Bari 4-mg or Bari 2-mg or Bari 1-mg vs PBO; Week 16	Sensitivity analysis
Skin Infections	Proportion of patients developing skin infections requiring antibiotic treatment	Fisher's exact	ITT	Bari 4-mg or Bari 2-mg or Bari 1-mg vs PBO; Week 16	Secondary analysis

Abbreviations: ANCOVA = analysis of covariance; Bari = baricitinib; ITT = intent-to-treat; mLOCF = modified last observation carried forward; MMRM = mixed model repeated measures; NRI = nonresponder imputation; PBO = placebo; pMI=placebo multiple imputation; PPS = per protocol set.

6.11.1. Primary Outcome and Methodology

The validated Investigator's Global Assessment for AD (IGA) uses the clinical characteristics of erythema, papulation/induration, oozing/crusting and lichenification to produce a single-item score ranging from 0 to 4. The primary analysis of the study is to test the null hypotheses that neither baricitinib 4-mg nor baricitinib 2-mg is superior to placebo when evaluating the proportion of patients achieving IGA of 0 or 1 at Week 16 in the ITT population. The analysis assumes that treatment response disappears after patients are rescued or permanently discontinue from treatment. This will serve as the primary estimand. In this estimand, missing data due to the application of the primary censoring rule and the occurrence of other non-censor intercurrent events will be imputed using the NRI method described in Section [6.4.1](#).

A supplemental estimand is to test the null hypotheses that neither baricitinib 4-mg nor baricitinib 2-mg is superior to placebo when evaluating the proportion of patients achieving IGA of 0 or 1 at Week 16 in the ITT population. This analysis assumes the treatment response disappears after patients permanently discontinue from treatment. In this supplemental estimand, missing data due to the application of the secondary censoring rule and the occurrence of other non-censor intercurrent events will be imputed using the NRI method described in Section [6.4.1](#).

A logistic regression analysis as described in Section [6.2.3](#) will be used for the comparisons. The odds ratio, the corresponding 95% CIs and p-value, as well as the treatment differences and the corresponding 95% CIs, will be reported.

Multiplicity controlled analyses will be performed on the primary and key secondary (see Section [4.2.1](#)) objectives to control the overall Type I error rate at a 2-sided alpha level of 0.05. A graphical approach will be used to perform the multiplicity controlled analyses as described in Section [6.6](#).

6.11.2. Secondary and Exploratory Efficacy Analyses

For secondary analysis, the null hypotheses is that neither baricitinib 4-mg nor baricitinib 2-mg is superior to placebo in the ITT population. These analyses assume treatment response disappears after patients are rescued or permanently discontinued from treatment and will serve as the primary estimand. In this estimand, missing data due to the application of the primary censoring rule and the occurrence of other non-censor intercurrent events will be imputed using the method described in [Table JAHL.6.1](#).

A supplemental estimand for secondary endpoints is to test the null hypotheses that neither baricitinib 4-mg nor baricitinib 2-mg is superior to placebo in the ITT population. These analyses assumes the treatment response disappears after patients permanently discontinue from treatment. In this supplemental estimand, missing data due to the application of the secondary censoring rule and the occurrence of other non-censor intercurrent events will be imputed using the method described in [Table JAHL.6.1](#).

A list of exploratory endpoints are provided in Section 4.2.2. There will be no adjustment for multiple comparisons for exploratory endpoints. The secondary and exploratory efficacy endpoints are detailed in [Table JAHL.6.4](#) and analyses are provided in [Table JAHL.6.5](#). Health outcomes analyses are described in Section 6.12.

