6.4. Handling of Dropouts or Missing Data

Intercurrent events (ICH E9 R1) are events which occur after the treatment initiation and make it impossible to measure a variable or influence how it would be interpreted.

Depending on the estimand being addressed, different methods will be used to handle missing data as a result of intercurrent events. Intercurrent events can occur through the following:

- application of one of the censoring rules (including after permanent study drug discontinuation or after rescue therapy)
- discontinuation
- missing an intermediate visit prior to discontinuation or rescue
- lost to follow-up.

Non-censor intercurrent events are events that are not due to the application of any censoring rule, i.e., the last 3 items in the list above.

Note that as efficacy and health outcome data can accrue after a patient permanently discontinues study drug or begins rescue therapy, specific general censoring rules to the data will be applied to all efficacy and health outcome observations subsequent to these events depending on the estimand being addressed. These specific censoring rules are described below.

The *primary censoring rule* will censor efficacy and health outcome data after permanent study drug discontinuation or after rescue therapy. This censoring rule will be applied to all continuous and categorical efficacy and health outcome endpoints. This censoring rule is equivalent to using all the data up to rescue.

A *secondary censoring rule* will only censor efficacy and health outcome data after permanent study drug discontinuation. This sensitivity analysis will include all observed values up to study drug discontinuation. The secondary censoring rule will be applied to primary and key secondary efficacy and health outcome endpoints as sensitivity analyses.

Table JAHL.6.1 describes the planned imputation methods for efficacy and health outcome endpoints with associated censoring rules. Sections 6.4.1 through 6.4.5 summarize the methodology of each imputation rule.

Table JAHL.6.1. Imputation Techniques for Various Variables

Efficacy and Health Outcome Endpoints	Imputation Method
IGA(0,1), EASI75, 4-point Itch NRS improvement, EASI90, SCORAD75	NRI ^{ab} , pMI ^a , Tipping point ^a
EASI percent change, ADSS Item 2 change, Skin Pain NRS change	MMRM ^{ab} , mLOCF ^a , pMI ^a
All remaining categorical measures	NRI ^a
All remaining continuous efficacy and health outcome measures	MMRM ^a , mLOCF ^a

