6.4.1. Nonresponder Imputation

A nonresponder imputation (NRI) method imputes missing values as non-responses and can be justified based on the composite strategy for handling intercurrent events (ICH E9 R1). This imputation procedure assumes the effects of treatments disappear after the occurrence of an intercurrent event defined by the associated censoring rule.

All categorical endpoints will utilize the NRI method after applying the primary censoring rule to patients who permanently discontinued study drug or were rescued (described in Section 6.4). Additionally, all primary and key secondary categorical endpoints will utilize NRI after applying the secondary censoring rule as sensitivity analyses. For analyses which utilize either of the censoring methods, randomized patients without at least 1 post-baseline observation will be defined as nonresponders for all visits.

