6.4.2. Mixed Model for Repeated Measures

Mixed Model for Repeated Measures analyses will be performed on continuous endpoints to mitigate the impact of missing data. This approach assumes missing observations are missing-at-random (missingness is related to observed data) and borrows information from patients in the same treatment arm taking into account both the missingness of data through the correlation of the repeated measurements.

Essentially MMRM estimates the treatment effects had all patients remained on their initial treatment throughout the study. For this reason, the MMRM imputation implies a different estimand (hypothetical strategy [ICH E9 R1]) than the one used for NRI on categorical outcomes.

All continuous endpoints will utilize MMRM after applying the primary censoring rule. As sensitivity analyses, all secondary continuous endpoints will also utilize MMRM after applying the secondary censoring rule (Table JAHL.6.1).

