6.12. Health Outcomes/Quality-of-Life Analyses

The general methods used to summarize health outcomes and quality-of-life measures, including the definition of baseline value for assessments are described in Section 6.1.

Health outcomes and quality-of-life measures will generally be analyzed according to the formats discussed in Section 6.11.

[Table JAHL.6.6](#) includes the descriptions and derivations of the health outcomes and quality-of-life measures.

[Table JAHL.6.7](#) provides the detailed analyses including analysis type, method and imputation, population, time point, and comparisons for health outcomes and quality-of-life measures.

Additional psychometric analyses will be performed by Global Patient Outcomes Real World Evidence at Lilly and documented in a separate analysis plan.

Table JAHL.6.6. Description and Derivation of Health Outcomes and Quality-of-Life Measures

Measure	Description	Variable	Derivation / Comment	Imputation Approach if Missing Components
Itch Numeric Rating Scale (NRS)	The Itch Numeric Rating Scale (NRS) is a patient-administered, 11-point horizontal scale anchored at 0 and 10, with 0 representing “no itch” and 10 representing “worst itch imaginable.” Overall severity of a patient’s itching is indicated by selecting the number that best describes the worst level of itching in the past 24 hours (Naegeli et al. 2015; Kimball et al. 2016). Refer to Section 6.2.2 for details on how to calculate the weekly score which will be used in the continuous analysis.	Itch NRS score	Single item; range 0-10. Refer to Section 6.2.2 on how to derive the visit score.	Refer to Section 6.2.2 on how to derive the weekly visit score.
		▪ Change from baseline in Itch NRS ▪ Percent change from baseline in Itch NRS	Change from baseline: observed Itch score – baseline Itch score % change from baseline: $100 \times \frac{\text{Observed score} - \text{Baseline}}{\text{Baseline}}$	Missing if baseline or observed value is missing.
		4-point Itch improvement in subgroup of patients with baseline Itch NRS ≥ 4	Change from baseline ≤ 4 and baseline ≥ 4	Missing if baseline is missing or < 4 or observed value is missing.

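### Does SAP 6.11.2 attach the wrong estimand to the continuous secondary endpoints, which are analysed by MMRM?

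*SAP*

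**What the plan says.** SAP 6.11.2 gives the secondary analyses one primary estimand: "These analyses assume treatment response disappears after patients are rescued or permanently discontinued from treatment and will serve as the primary estimand". It then sends missing data to Table JAHL.6.1. Its supplemental paragraph, which uses the secondary censoring rule, repeats the idea for discontinuation alone: "These analyses assumes the treatment response disappears after patients permanently discontinue from treatment".

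Table JAHL.6.1 assigns NRI to the categorical endpoints. For EASI percent change, ADSS Item 2 change and Skin Pain NRS change it lists MMRM (under both censoring rules), mLOCF and pMI. SAP 6.2.3 makes MMRM the main method for all continuous efficacy and health outcome variables.

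The two methods are described separately. On NRI, SAP 6.4.1 says: "This imputation procedure assumes the effects of treatments disappear after the occurrence of an intercurrent event defined by the associated censoring rule". On MMRM, SAP 6.4.2 says: "Essentially MMRM estimates the treatment effects had all patients remained on their initial treatment throughout the study". It adds that "the MMRM imputation implies a different estimand (hypothetical strategy [ICH E9 R1]) than the one used for NRI on categorical outcomes".

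Skin Pain NRS and ADSS Item 2 are listed as health outcomes in Table JAHL.6.7. For these, 6.11.2 says only: "Health outcomes analyses are described in Section 6.12". Section 6.12 points back: "Health outcomes and quality-of-life measures will generally be analyzed according to the formats discussed in Section 6.11".

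**The concern.** Read alone, 6.11.2 says that a confirmatory result on EASI percent change counts benefit as lost once a patient is rescued or stops study drug. MMRM does not do that. Under the primary censoring rule it treats the later values as missing at random and estimates what would have been seen had treatment continued. The stated estimand and the invoked method therefore disagree.

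What is at stake is how a positive continuous result may be described. A reader who took 6.11.2 at its word could believe the result already penalises rescue and discontinuation, when it does not. The SAP itself says in 6.4 that the handling of missing data depends on the estimand addressed, so a wrong label is a fair thing to question.

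**Working it through.** The plan states no figure to reproduce here. The check compares the sections, counts the endpoints affected, and asks whether anything computed depends on the sentence.

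**1. Sections side by side**

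| Place in SAP | Applies to | After rescue or discontinuation |
|---|---|---|
| 6.4.1 | categorical, NRI | effect taken as lost (composite strategy) |
| 6.4.2 | continuous, MMRM | effect as if initial treatment had continued (hypothetical strategy) |
| 6.11.1 | IGA primary endpoint, NRI | response taken as lost, which matches 6.4.1 |
| 6.11.2 | all secondary efficacy endpoints | response taken as lost, which matches 6.4.1 but not 6.4.2 |

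The estimand paragraphs of 6.11.2 closely follow those of 6.11.1. The pointer to the NRI section has become a pointer to Table JAHL.6.1, while the assumption stayed as it was. That pattern suggests a drafting carry-over rather than a second choice of estimand; this is an inference from the text.

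**2. Scope within the multiplicity family (SAP 6.6)**

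- Family: 12 endpoints × 3 doses = 36 hypotheses.
- Continuous: endpoints 4 (EASI percent change), 8 (Skin Pain, Week 16), 9 (ADSS Item 2, Week 16) and 11 (ADSS Item 2, Week 1). 4 × 3 = 12, and 12/36 = 33.3%.
- Listed under 6.11 (Table JAHL.6.5): EASI percent change only. 1 × 3 = 3, and 3/36 = 8.3%. On the literal 4-mg and 2-mg null it is 1 × 2 = 2.
- Listed under 6.12 (Table JAHL.6.7): 3 × 3 = 9. These are reached only if the sentence in 6.12 about formats is read as importing an estimand.
- Outside the family, SCORAD and BSA change are also continuous secondary endpoints analysed by MMRM in Table JAHL.6.5.

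**3. Would the two estimands differ in value?**

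They could. The documents give no event rates or mean changes, so the following values are assumed. Take a mean EASI change without events of −60% on active and −35% on placebo, and zero change after an event. The hypothetical difference is −60 − (−35) = −25 points. If response is lost, the difference is (1 − r_a)(−60) − (1 − r_p)(−35), where r_a and r_p are the event rates on active and placebo:

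- 20% and 20%: −48.0 + 28.0 = −20.0
- 30% and 30%: −42.0 + 24.5 = −17.5
- 30% and 50%: −42.0 + 17.5 = −24.5
- 40% and 60%: −36.0 + 14.0 = −22.0

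On these assumptions the gap runs from 0.5 to 7.5 points, so the label would matter if it drove the computation.

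**4. Does it drive the computation?**

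It does not. The method comes from Table JAHL.6.1, the model from 6.2.3 and the censoring from 6.4. The testing order and alpha come from 6.6. None of these refers to the estimand sentence in 6.11.2. Deleting or correcting it leaves every estimate, standard error and p-value as it was.

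**5. Is the other question already addressed?**

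It is, at Week 16. SAP 6.4.4 plans pMI under the primary censoring rule for the key secondary endpoints, on the assumption that the drug gives no benefit after the event. Table JAHL.6.2 supplies seeds for EASI percent change, Skin Pain NRS and ADSS Item 2. This is not identical to a return to zero change, because the imputed values follow placebo behaviour, but it shows how the continuous results hold up without assuming continued benefit.

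**The case for a change.** The strongest case for a correction is that 6.11.2 is where the SAP formally names the primary estimand for secondary endpoints, and the SAP sets no order of precedence between it and 6.4.2. The section also points to Table JAHL.6.5, which lists EASI percent change by MMRM as a key secondary analysis, so it cannot be read as meaning categorical endpoints only. A correction would take a few sentences and use content the SAP already has.

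Most of this stands as a description of the text: for EASI percent change the sentence is inaccurate, and so is the supplemental one. The consequence does not follow as easily. A misreport would need an author to take one general sentence and pass over 6.4.2, which names both the strategy and its difference from NRI. The method-specific text qualifies the general sentence, and an analyst going from 6.11.2 to Table JAHL.6.1 and on to the subsections it summarises arrives at the right description.

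Nor is a replacement sentence as simple as it looks. The secondary rule "will only censor efficacy and health outcome data after permanent study drug discontinuation". It would be tempting to say that data after rescue are then used as observed. That holds only while study drug continues, as with topical rescue; Protocol 7.7.3 requires permanent discontinuation with oral systemic rescue, so those later data are censored under the secondary rule too. Missed visits and loss to follow-up, which SAP 6.4 also lists as intercurrent events, would need their own statement.

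**Conclusion.** The inconsistency is genuine but clerical. It directly affects the description of EASI percent change (3 of 36 family hypotheses, or 2 on the literal null) and of the continuous SCORAD and BSA endpoints outside the family. It reaches at most 12 of 36, and the other 9 rest on a strained reading of 6.12. The numerical effect on any planned result is nil.

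No change to the plan follows because nothing would be gained. The analysis is unambiguous, its estimand is stated correctly in 6.4.2, and the Week 16 pMI already covers the no-continued-benefit assumption for the continuous key secondary endpoints. This rests on two assumptions: that analysts take the method from Table JAHL.6.1 and 6.2.3, as 6.11.2 itself directs through its reference to the table, and that the report describes the continuous results in the terms of 6.4.2.
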